4.3.3 Sensitivity analysis

In addition to planned protocol analysis of the primary endpoint, if cohort assignment based on local laboratory's cPRA value collected at screening visit varies from the corresponding central laboratory's baseline cPRA value in greater than 10% of the efficacy-evaluable participants per cohort, a sensitivity analysis of the primary efficacy endpoint will be conducted assigning participants to the respective cohort based on the central laboratory's cPRA value.

4.3.4 Supplementary analyses

Not applicable.

4.3.5 Subgroup analyses

Not applicable.

4.4 SECONDARY ENDPOINT(S) ANALYSIS

4.4.1 Key/Confirmatory secondary endpoint(s)

No key/confirmatory secondary endpoint.

4.4.2 Supportive secondary endpoints

4.4.2.1 Definition of endpoints

The following secondary endpoints in the Phase 2 portion of the study are defined below, with the exception of PK parameters and immunogenicity/ADA against isatuximab which are described in [Section 4.8.1](#) and [Section 4.8.2](#), respectively:

DoR per central laboratory assessment

DoR (based on central laboratory assessment): defined as time from laboratory sample collection date used in determining a participant to be a responder up to the laboratory sample collection date when participant is no longer meeting any response criterion (ie, non-responder) or the date of death due to any cause, whichever occurs first.

For participants with ongoing response at the time of the analysis, DoR will be censored at the date of the last available laboratory assessment showing response. Non-responders will be excluded in the DoR summaries.

For responders meeting more than 1 criterion, DoR will be calculated from: [(earliest of start dates) up to (latest of end dates) + 1] across any response criteria durations.

For responders having multiple DoRs within the same criterion but with gaps, only the 1st DoR (or 1st set of DoRs for those meeting more than 1 criterion) will be summarized. A sensitivity analysis may be performed using the longest DoR (in lieu of 1st DoR), if applicable.

Proportion of participants and duration achieving target cPRA per local laboratory assessment (using OPTN-calculated and using locally reported cPRA values)

Proportion of participants achieving target cPRA: will be summarized separately for cPRA values, based on OPTN calculator and based on locally reported values

Duration of achieving target cPRA: defined as time from laboratory sample collection date of achieving target cPRA the first time up to the laboratory sample collection date when no longer achieving target cPRA or the date of death due to any cause, whichever occurs first.

Participants who retain their target cPRA values will be censored at the date of the last available laboratory assessment achieving their target cPRA. Participants who do not achieve target cPRA will be excluded from the analysis.

For participants with multiple durations (with gaps), only the 1st duration will be summarized. A sensitivity analysis may be performed using the longest duration (in lieu of the 1st duration), if applicable.

Refer to [Section 5.4.2, Table 8](#) for a table of target cPRA.

Number of anti-HLA-antibody with baseline MFI \geq 3000 reduced to $<$ 2000 as measured in a SAB assay per central laboratory assessment

Reduction of anti-HLA-antibody is defined similarly as in RR criterion 3 ([Section 4.3.1](#)), and will be summarized by the proportion of participants with pre-specified ranges of anti-HLA-antibody reduction (eg, none, 1-5, >5-10, >10-15, ... >x).

Transplantability including time to first transplant offer, time to transplant, and number of transplant offers, if applicable

Time to first transplant offer: defined as time from date of first IMP dose up to date of first transplant offer. Study eCRF folder/page for transplant offer: TRANSPLANT/TRANSPLANT STATUS

Time to transplant: defined as time from date of first IMP dose up to date of kidney transplant on/after first IMP start date. Study eCRF FOLDER/page for date of kidney transplant surgery during study: TRANSPLANT/TRANSPLANT STATUS; KIDNEY TRANSPLANT SURGERIES [Transplant and Patient status subcategory=During study, and corresponding Date of kidney transplant]

Participants who do not receive any transplant offer or any transplant, and:

- who died will be censored at the longest follow-up date across all participants in the study prior to the analysis cut-off date.
- who are still alive will be censored at the participant's last laboratory assessment date collected in the study or at the analysis cut-off date, whichever is earlier.

Time to first AMR episode and rate of AMR (if applicable)

Time to first AMR: defined as time from date of first IMP dose up to date of biopsy with first AMR. Study eCRF FOLDER/page for date of biopsy with AMR: TRANSPLANT/GRAFT REJECTION BIOPSY

Transplanted participants without any AMR will be censored at the participant's last assessment/contact date collected in the study or at the analysis cut-off date, whichever is earlier. Participants who do not receive a transplant in the study will be excluded from this analysis.

Rate of AMR: defined as proportion of participants with AMR field ticked as "yes" based on graft rejection biopsy eCRF page. Study eCRF FOLDER/page for AMR: TRANSPLANT/GRAFT REJECTION BIOPSY

Graft survival rate at 6 months post-transplant (if applicable)

Graft survival rate at 6 months post-transplant: defined as proportion of participants with graft survival status at \leq 6 months post-transplant="Functioning". Study eCRF FOLDER/page for date of biopsy with AMR: TRANSPLANT/GRAFT SURVIVAL AT LESS THAN OR EQUAL TO 6 MONTHS

In addition, the proportion of participants with a functioning graft beyond 6 months post-transplant may be tabulated, if data are available. An adhoc analysis of graft survival may also be performed using the Kaplan-Meier method.

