Coagulation	X (≤14 days prior to first IMP)	As clinically indicated											See Section 10.2				
Blood typing interference test ⁱ	X (≤14 days prior to first IMP)					X ^j (IAT)				X ⁱ (IAT)			See Section 10.10				

Procedure	Screening (up to 28 days before Day 1)	Treatment Period (12 weeks)								Site Visit FUP (26 weeks) ^a	E/D ^b	Extended FUP ^c	Notes All on-treatment procedures should be performed prior to IMP administration unless indicated otherwise				
		Cycle 1 (28 Days)				Cycle 2 (28 days)		Cycle 3 (28 days)									
		D1	D8	D15	D22	D1	D15	D1	D15								
Time Window (days)		±1	±1	±1	±1	±2	±2	±2	±2	±7	±7	±7					
cPRA and SAB assay (local laboratory assessment)	X	Perform as per local standard of practice												For unacceptable antigens, use MFI ≥2000 as positivity cut-off, and report cPRA to 2 decimal point (eg, 99.90%) See Section 8.1.2			
Blood draw for cPRA and SAB assay (central laboratory assessment)		X ^j				X		X		X (every 4 weeks) ^k	X			Refer to laboratory manual for details			
Blood draw for serum immunoglobulin levels (central laboratory assessment)		X ^j						X		X (Week 17 only) ^k	X ^l			Refer to laboratory manual for details			
Blood draw for immune cell profiling (central laboratory assessment)		X ^j						X		X (Week 17 only) ^k	X ^l			Refer to laboratory manual for details			
Blood draw for functional immune cell assay (central laboratory assessment)		X ^j						X		X (to be collected on Site Visit FUP Week 1 or E/D, if C3D1 sample not collected)				Refer to laboratory manual for details			
Isatuximab		X	X	X	X	X	X	X	X								
PK/ADA		See Pharmacokinetic/ADA Flowchart												See Section 1.3.1			

Procedure	Screening (up to 28 days before Day 1)	Treatment Period (12 weeks)								Site Visit FUP (26 weeks) ^a	E/D ^b	Extended FUP ^c	Notes All on-treatment procedures should be performed prior to IMP administration unless indicated otherwise				
		Cycle 1 (28 Days)				Cycle 2 (28 days)		Cycle 3 (28 days)									
		D1	D8	D15	D22	D1	D15	D1	D15								
Time Window (days)		±1	±1	±1	±1	±2	±2	±2	±2	±7	±7	±7					
AE review	X	←=====→								X (beyond 30 days after last dose of IMP: only ongoing related AEs, new related AEs until resolution/ stabilization)	Stabilization is defined as an AE ongoing without any change for at least 3 months						
SAE review	X	←=====→								X (beyond 30 days after last dose of IMP: only ongoing SAEs, new related SAEs until resolution/ stabilization)							

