- o Collect the following information: Start and end date(s) when listed as active candidate on the waitlist for kidney transplant (if status has changed), virtual or donor-specific cross matching results, dates of all transplant offers (if any, indicate whether offers were accepted and reasons of rejecting offers), solid organ transplant surgery, participant survival status, graft survival status, dates of biopsy proven acute rejection episodes (antibody mediated and/or T-cell mediated), and estimated glomerular filtration rate (eGFR) using the Modification of Diet in Renal Disease (MDRD) equation.

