9.4.1 Efficacy analyses

Analysis of primary efficacy endpoint:

- In Phase 2, the RR by cohort will be summarized using descriptive statistics. A 95% 2-sided confidence interval will be computed using the Clopper-Pearson method ([Table 9](#)).

Analyses of secondary endpoints:

- All secondary endpoints (if applicable) during Phase 2 will be summarized descriptively and presented by cohort. Categorical variables (eg, rates and proportions) will be tabulated

via frequency distributions. Continuous variables (eg, change from baseline) will be summarized by providing the number of observations (n), mean, median, standard deviation, minimum, and maximum. Duration of response and other time to event variables will be analyzed using the Kaplan-Meier method ([Table 9](#)). Participants not reaching an event will be censored at their last follow-up visit.

- No hypothesis/significance testing will be performed.

Table 9 - Efficacy analyses

Endpoint	Statistical Analysis Methods
Primary: Response rate (per central laboratory)	Descriptive statistics and Clopper-Pearson method
Secondary:	

 • Rate/Proportion of participants: 
 - achieving target cPRA (per local laboratory) - with AMR (if applicable) - with graft survival at 6 months post-transplant (if applicable) 	Descriptive statistics

 • Number of: 
 - anti-HLA-antibody eliminated (per central laboratory) - transplant offers (if applicable) 	Descriptive statistics

 • Duration of: 
 - response (DoR) (based on central laboratory) - achieving target cPRA (based on local laboratory) 	Kaplan-Meier method

 • Time to event: 
 - first transplant offer - transplant (if applicable) - first AMR episode (if applicable) 	Kaplan-Meier method
Tertiary/Exploratory	Will be described in the SAP and finalized before the database lock.

Abbreviations: AMR = antibody mediated rejection, cPRA = calculated panel reactive antibodies, DoR = duration of response, HLA = human leukocyte antigen, SAP = statistical analysis plan.

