4.4.2.2 Main analytical approach

All secondary efficacy endpoints (if applicable) during Phase 2 will be summarized descriptively and presented by cohort. Categorical variables (eg, rates and proportions) will be tabulated via frequency distributions (ie, number and percents). Continuous variables (eg, change from baseline) will be summarized by providing the number of observations (n), mean, median, SD, minimum, and maximum.

DoR and other time to event variables will be analyzed using the Kaplan-Meier method (ie, median and associated 95% confidence interval). No hypothesis/significance testing will be performed.

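### A death long after the last central sample counts as the end of response, so DoR can include unmeasured time and one late death can set the median

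*SAP*

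**What the plan says.** For DoR per central laboratory, SAP 4.4.2.1 runs the clock from the sample that establishes response to the sample "when participant is no longer meeting any response criterion (ie, non-responder) or the date of death due to any cause, whichever occurs first". For a response still ongoing at the analysis, "DoR will be censored at the date of the last available laboratory assessment showing response". The population is responders only: "Non-responders will be excluded in the DoR summaries". SAP 4.4.2.2 states the summary: "DoR and other time to event variables will be analyzed using the Kaplan-Meier method (ie, median and associated 95% confidence interval". SAP 4.4.2.1 sets no maximum gap before a death and has no DoR rule for transplant.

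Protocol 9.4.1 words the censoring differently: "Participants not reaching an event will be censored at their last follow-up visit".

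In the Schedule of Activities (Protocol 1.3), the row "Blood draw for cPRA and SAB assay (central laboratory assessment") has entries at C1D1, C2D1, C3D1, every 4 weeks in site visit follow-up, and at early discontinuation (E/D). It has none in extended follow-up. Footnote o of the same schedule, covering the later participant and transplant status, includes "participant survival status, graft survival status". Under Protocol 4.1, a participant who goes to transplant has an E/D visit if feasible and then enters extended follow-up.

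The local-laboratory duration of target cPRA uses the same death clause, ending "when no longer achieving target cPRA or the date of death due to any cause, whichever occurs first".

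**The concern.** Protocol 3.1 gives antibody rebound as the reason for measuring DoR. Rebound can be seen only while samples are taken. Under the SAP rule, two responders with the same samples, both in response at the last one, get different durations solely because one of them later dies. The survivor stops contributing at the last sample; the other is credited with response up to the date of death.

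The added time is not neutral. Protocol 6.5 lifts its ban on other desensitization procedures at the end of site visit follow-up, at E/D or at transplant, and Protocol 6.7 recommends immunosuppression after transplant. Antibody levels in that interval are neither measured nor attributable to isatuximab alone.

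With a planned minimum of 12 participants per cohort, and only responders in the analysis, one such death may be the last observation at risk. The reported median would then be a date of death rather than a measured duration of response.

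**Working it through.** **Stated durations.** Screening 28 days, treatment 12 weeks and site visit follow-up 26 weeks (Protocol 4.1): 28/7 + 12 + 26 = 42 weeks. This reproduces the protocol's figure of about 42 weeks. The protocol gives about 78 weeks with extended follow-up, so 78 − 42 = 36 weeks lie in extended follow-up.

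**Longest response that on-schedule central samples can show.**
- C2D1 is Day 29, C3D1 is Day 57 and C3D15 is Day 71.
- Follow-up Week 1 is 15 days after C3D15 (Schedule of Activities, footnote a): 71 + 15 = Day 86.
- Week 25 is 24 weeks later: 86 + 168 = Day 254.
- From C2D1: (254 − 29)/7 = 32.1 weeks. From C3D1: (254 − 57)/7 = 28.1 weeks.
- Protocol 6.6.2 permits delays of up to 56 days. With a delay of that size before Cycle 3, the first figure becomes (225 + 56)/7 = 40.1 weeks.

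**Unsampled time that a death can add.** At about 78 weeks in total, the participant is at (78 − 4) × 7 = Day 518 from first dose. After Week 25 that leaves (518 − 254)/7 = 37.7 weeks. If a transplant at Day 60 (assumed) ends sampling, it leaves (518 − 60)/7 = 65.4 weeks.

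**Effect on the median (assumed data).** Take 8 responders. Three lose response at weeks 12, 16 and 20; four living responders are censored at week 32; one is in response at its week-32 sample and dies at week 60. If response began at C2D1, that death falls on Day 29 + 420 = 449, inside the 518 days.

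| Week | At risk | S(t), SAP rule | S(t), death censored at last sample |
|---|---|---|---|
| 12 | 8 | 7/8 = 0.875 | 0.875 |
| 16 | 7 | 0.875 × 6/7 = 0.75 | 0.75 |
| 20 | 6 | 0.75 × 5/6 = 0.625 | 0.625 |
| 60 | 1 | 0.625 × 0/1 = 0 | no step |
| Median | | 60 weeks | not reached |

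Transplant variant: the same death at week 60, but the last sample was at week 8 of response. The SAP median is still 60 weeks. With censoring at week 8 the curve is 6/7 = 0.857, then × 5/6 = 0.714, then × 4/5 = 0.571, and the median is not reached.

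**When the median does not move.** With a fourth loss at week 24, the curve is 0.625 × 4/5 = 0.5 and the median is 24 weeks under both rules. With the losses spaced 4 weeks apart from week 12 and a death at week 60, the SAP median was 60 weeks for 6 responders with 0 or 2 losses, for 8 with 0, 2 or 3, and for 12 with 0, 2, 3, 4 or 5. Censoring at the last sample gave not reached in each of these. With 3 losses among 6 the median was 20 weeks under either rule.

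**How often.** The documents give no mortality rate. Assuming 3% to 15% a year, the chance of at least one death among k ongoing responders in 36 weeks is 1 − exp(−rate × k × 36/52). For k = 4 this is 8% to 34%; for k = 8 it is 15% to 56%.

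**The case against.** - **Low stakes.** DoR is a supportive secondary endpoint, no test is planned, and the primary response rate with its Clopper-Pearson interval does not use it. This stands, and it limits the weight of the point.
- **Several conditions must coincide.** A responder must still be in response at the last sample, die well after it but before cut-off, and be in a cohort where fewer than half of responders have lost response. Cut-off is planned 26 weeks after the last participant completes treatment, so late enrollees have little unsampled follow-up unless it is extended. This stands; the 36-week window is not everyone's.
- **The interval would warn the reader.** In the example, log-log limits run from 12 weeks to not estimable (at week 12 the lower limit for S is 0.387, already below 0.5; no estimable upper limit falls to 0.5). A careful reader would see the instability, but the point estimate would still be one that sampling could not have shown.
- **Death as an event is conservative.** This is fair when death closely follows a sample, and such deaths should stay events. It does not carry over to a death that occurs after all survivors have been censored. Nor is the distortion all one way: a curve falling to 0 can look worse than a plateau at 0.625 with no median.

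A reader might also infer that the SAP mishandles every transplanted responder. It does not: no central draw is scheduled after transplant, so a living transplanted responder in response is already censored at the last sample. Nor can one say that local cPRA is unmeasured after Week 25. Local assays follow local practice, with no fixed stopping point.

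**Conclusion.** The point holds as a defect in the DoR rule with conditional consequences. The text names death as an event without limit, and the sentence on ongoing response does not override that.

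If fewer than half of responders have lost response when sampling ends, one late death can place the median beyond what was measurable: 60 weeks in the example, against about 32 weeks on schedule (about 40 weeks with a 56-day delay before Cycle 3). If half or more have lost response, the median is unchanged and only the tail is affected.

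The response counts, event times and mortality range are assumptions; the sampling schedule and the rule are not. The documents do not support reading this as a threat to the primary result, as a certain distortion of the DoR median, or as a bias that always favours the drug. It should be corrected before the analysis, in proportion to a descriptive endpoint.

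**What to change.** In SAP 4.4.2.1:

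1. Count death as a DoR event only if it falls within a pre-stated gap of the last central sample showing response, for example one scheduled interval plus the visit window (4 weeks + 7 days). Otherwise censor at that sample. Apply this equally to transplanted responders who later die.
2. List deaths beyond the gap separately, with the time since the last sample and any transplant date.
3. Keep the present rule as a sensitivity analysis.
4. For the local-laboratory duration of target cPRA, censor a death that falls beyond a pre-stated gap from the last local sample. This gap needs its own justification because local sampling has no fixed schedule.
5. Reconcile the SAP censoring date with the last-follow-up-visit wording in Protocol 9.4.1.

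The cost is SAP wording and a small programming change, with no new data. The median may read not reached, late deaths no longer end response in the main analysis, and the length of the gap is a convention that the documents do not supply.

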Prior/concomitant/post medication ^m	X	←=====→								X	X	X	See Section 6.5				
Participant/Transplant (if applicable) Status	X ⁿ	X ⁿ								X ^o	X ^o						

Abbreviations: ADA = anti-drug antibody, AE = adverse event, CMV = cytomegalovirus, cPRA = calculated panel reactive antibodies, D = Day, EBV = Epstein-Barr virus, ECG = electrocardiogram, E/D = early discontinuation, FUP = follow-up period, HBV = hepatitis B virus, hCG = human chorionic gonadotropin, HCV = hepatitis C virus, HIV = human immunodeficiency virus, HLA = human leukocyte antigen, ID = identification number, IMP = investigational medicinal product, MFI = mean fluorescence intensity, PK = pharmacokinetics, SAB = single antigen bead, SoA = Schedule of Activities, SAE = serious adverse event, WOCBP = women of childbearing potential.

- a Week 1 visit for site visit FUP will occur 15 days after Cycle 3 Day 15 (± 7 days), or 15 (± 7 days) after the last dose of IMP if participant discontinued IMP. Depending on local arrangements and preference of the Investigator, site visit FUP procedures may be performed at the study site or at the participant's home by a health care professional. Study procedures not performed at the study site must also be documented in the source documents and recorded in the appropriate pages of the eCRF by the study site.
- b For E/D, study procedures will be performed 30±7 days after last IMP administration if discontinued study during treatment period, or within 30 days if discontinued during site visit FUP. Participants who discontinued IMP but remain on the study and proceed to complete site visit FUP do not need to complete E/D. Participants who wish to proceed to transplantation when a compatible donor becomes available while on study must discontinue IMP immediately, and complete an E/D visit prior to transplantation if clinically feasible, and proceed to extended FUP.
- c In addition to the phone calls every 90 days, study site will collect information per the SoA throughout the extended FUP.
- d Vital sign assessment includes blood pressure, pulse rate, temperature, and respiratory rate. During the treatment period, vital signs should be obtained prior to start of each IMP infusion, 1 hour after start of infusion, at the end of infusion, and during the infusion if clinically indicated.

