Duration of response (assessed both locally and centrally) is included as a secondary endpoint to address potential antibody rebound concern, which is commonly observed with current desensitization protocols. If applicable, transplantability and post-transplant outcomes will also be captured as secondary endpoints.

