4.3 PRIMARY ENDPOINT(S) ANALYSIS

4.3.1 Definition of endpoint(s)

The primary endpoint in the Phase 1 portion of the study will focus on safety, ie, AEs/SAEs and laboratory abnormalities. Analysis details of these safety parameters are presented in [Section 4.7.2](#) and [Section 4.7.3.1](#).

In the Phase 2 portion of the study, the primary efficacy endpoint will be RR, to be defined as the proportion of participants meeting at least one of the predefined desensitization efficacy criteria, from baseline up to 26 weeks after treatment period, measured by SAB assay per central laboratory assessment as follows:

- Reduction in cPRA resulting in at least 100% increase of likelihood of finding a compatible donor for target cPRA
- Reduction in antibody titer ($\geq 75\%$ reduction from baseline) to achieve target cPRA
- Elimination of ≥ 1 anti-HLA-antibody (ie, MFI reduced to < 2000) as measured by a SAB assay, for antibodies with baseline MFI ≥ 3000

RR criterion 1: target cPRA

The target cPRA, defined as the reduction of cPRA required to achieve at least 100% increase of likelihood of compatible donor (LCD), is calculated according to the following equation:

$$LCD = 1 \text{ in } \frac{1}{1 - cPRA}$$

Participants with baseline cPRA 100.00% will be assigned with cPRA 99.99% for computational purpose. In addition, cPRA values will be rounded to 2 decimal places prior to LCD calculation ($\geq xx.xx5$ =round up, $< xx.xx5$ =round down).

RR criterion 2: antibody titer

Antibody titer is defined as the last dilution of serum at which positive results is obtained (eg, MFI ≥ 2000). To potentially meet the second RR criterion, serial dilution of the serum collected at baseline is performed until the target cPRA is achieved. If subsequent post-treatment serum is diluted at $\geq 75\%$ reduction from the baseline dilution that achieved target cPRA, and again meet target cPRA anytime within the 26-week post-treatment period, participant will have met RR criterion 2.

RR criterion 3: anti-HLA-antibody

An anti-HLA-antibody is considered to be eliminated if its MFI is reduced to < 2000 at post-treatment. Only antibodies with baseline MFI ≥ 3000 will be included for assessment under this criterion.

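### The duration-of-response rule for responders who meet more than one criterion can count time when no criterion was met

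*SAP*

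**What the plan says.** SAP section 4.4.2.1 makes three statements about DoR by central laboratory.

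- **Definition.** DoR starts at the sample that makes the participant a responder. Its end is given as "laboratory sample collection date when participant is no longer meeting any response criterion (ie, non-responder) or the date of death due to any cause"; the earlier of the two applies. An ongoing response is censored at the last sample showing response.
- **More than one criterion.** "DoR will be calculated from: [(earliest of start dates) up to (latest of end dates) + 1] across any response criteria durations".
- **Gaps.** Where a responder has several durations under one and the same criterion, "only the 1st DoR (or 1st set of DoRs for those meeting more than 1 criterion) will be summarized". A sensitivity analysis on the longest DoR is optional.

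SAP section 4.4.2.2 summarizes DoR by cohort with a Kaplan-Meier median and 95% confidence interval, without testing. Protocol section 3.1 gives the purpose: "Duration of response (assessed both locally and centrally) is included as a secondary endpoint to address potential antibody rebound concern".

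**The concern.** The definition works at participant level: once a sample meets no criterion, the response is over. The rule for several criteria takes the outer span of all durations and does not ask whether they join up. Where they do not, the span includes central samples at which the participant was a non-responder.

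The gap rule does not clearly prevent this. It is triggered by repeated durations under a single criterion, so a participant with one duration under each of two criteria, separated in time, falls outside it. It also leaves the first set of durations undefined. That could mean the first continuous block, which agrees with the definition, or the first duration of each criterion, which does not.

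At stake is an endpoint included to show antibody rebound. For affected participants a documented loss is bridged over or turned into censoring, always towards longer DoR. Two programmers could also derive different values from the same samples.

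**Working it through.** The SAP states no DoR figure to reproduce, so the check applies both texts to response patterns on the planned sampling days.

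**Sampling days.** Cycles last 28 days (Protocol 1.1), so Cycle 2 Day 1 is Day 29, Cycle 3 Day 1 is Day 57 and Cycle 3 Day 15 is Day 71. Footnote a of the Schedule of Activities says "Week 1 visit for site visit FUP will occur 15 days after Cycle 3 Day 15", so follow-up Week 1 is 71 + 15 = Day 86. The schedule has central samples at Cycle 2 Day 1, at Cycle 3 Day 1 and every 4 weeks in follow-up. Taking Week 1 as the first follow-up draw gives Days 29, 57, 86, 114, 142, 170, 198, 226 and 254 (86 + 6 × 28 = 254, Week 25). These are nominal days, ignoring visit windows.

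**Formulas.**
- Definition: first later sample with no criterion met − first sample with any criterion met + 1. The SAP's definition does not state the + 1; it is added so that both counts are comparable.
- Rule as written: latest end date over criteria − earliest start date + 1. A criterion's end date is the first sample at which it is lost, or the last sample (censored) if it is still met.

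| Pattern (criteria X and Y) | Definition | Rule as written |
|---|---|---|
| Overlapping: X met Days 29–86, Y met Days 57–114, lost at 142 | 142 − 29 + 1 = 114 | 114 |
| Abutting: X met Days 29–57, Y met Days 86–114, lost at 142 | 114 | 114 |
| X alone, met Days 29–57, lost at 86, later regained | 86 − 29 + 1 = 58 | 58 (first duration) |
| Separate: X met Days 29–57, lost at 86; Y met Days 142–170, lost at 198 | 58 | 198 − 29 + 1 = 170 |
| Separate, Y still met at Day 254 | 58, event | 254 − 29 + 1 = 226, censored |
| Separate, Y lost at 198, X met again at Days 142 and 170 | 58 | 58 if the first set is the first continuous block; 170 if it is the first duration of each criterion |

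In the fourth row the difference is 170 − 58 = 112 days. Of these, 142 − 86 = 56 days have no criterion met (samples at Days 86 and 114 negative), and 198 − 142 = 56 days belong to a second response.

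**Can the durations be separate?**
- Criterion 1 normally brings criterion 3, because cPRA and antibody elimination both use the MFI 2000 cut-off. The exception is an antibody with baseline MFI from 2000 to below 3000, which criterion 3 ignores.
- Criterion 1 also ordinarily brings criterion 2: if neat serum reaches target cPRA, diluted serum usually does too.
- Criteria 2 and 3 are less tied. Criterion 2 judges the whole antibody profile, usually in diluted serum; criterion 3 needs one antibody specificity to fall below 2000. Criterion 2 can also be met late (SAP 4.3.1): "again meet target cPRA anytime within the 26-week post-treatment period, participant will have met RR criterion 2".

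Separate durations are therefore most plausible for criterion 2 against criterion 3, or when a criterion is first met after criterion 3 was lost.

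**Effect on the median.** With an assumed 12, 6 or 3 responders in a cohort, each is 1/12 = 8%, 1/6 = 17% or 1/3 = 33% of the DoR sample. As a hypothetical case, take six responders with events at 58, 58, 86, 114, 142 and 170 days. With the median as the first time the curve is at or below 0.5, it is 86 days (survival 4/6 after Day 58, 3/6 at Day 86). Recode one 58-day loss as censored at 226 and survival is 5/6, 4/6, 3/6 at 58, 86, 114: median 114. Recode both and it is 5/6, 4/6, 3/6 at 86, 114, 142: median 142.

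**The case against.** The strongest reply is that the section should be read as a whole. The definition comes first and governs, the outer-span sentence only explains how to combine criteria under it, and the gap sentence keeps only the first set. On that reading the first set is the first continuous block and nothing is wrong except loose wording. This reading is possible, but the text does not require it. The SAP does not say that the definition overrides the more specific rule, and the gap sentence is not triggered by a gap between different criteria.

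The second reply is rarity. The example needs full loss at Day 86, 15 days after the last planned dose, and a different criterion newly met at Day 142, 71 days after it. Other desensitization is prohibited during site-visit follow-up (Protocol 6.5). Assay noise could produce such a course, but Protocol 3.1 expects MFI variability below 25% and uses the gap between 3000 and 2000 as a buffer. This stands: the documents give no frequency, and it may be low.

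The third reply is consequence. DoR is descriptive and untested, and one changed value moves a Kaplan-Meier median only if it shifts where the curve crosses 50%. This also stands, and it limits the weight of the point.

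**Conclusion.** The rule is wrong as written: followed literally, it contradicts the SAP's own definition whenever a responder's durations under different criteria are separate. In the worked case DoR becomes 170 days instead of 58, or an event at 58 days becomes censoring at 226. Overlapping durations, abutting durations and recurrence within a single criterion are not affected.

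The figures are illustrations on nominal sampling days, not an expected bias. The six-responder median is hypothetical and the responder counts are assumed. The point still deserves correction before analysis because the error has one direction, the endpoint is meant to detect rebound, and cohorts may have as few as 12 participants. Response rate, alpha, sample size and the local target-cPRA duration, which has its own first-duration rule, are unaffected. Confidence is medium because frequency is unknown and a benign reading exists.

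**What to change.** Revise SAP section 4.4.2.1 as follows:

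- At each central sample, derive response as at least one criterion met. Run DoR from the first such sample to the first later sample with no criterion met, or death. Censor at the last sample showing response if neither occurs.
- Apply the earliest-start, latest-end calculation only to durations that overlap or abut.
- Define the first set of durations as the first continuous set, across criteria as well as within one.
- As a minor addition, use the same day-count for all responders; at present the + 1 is stated only for those meeting more than one criterion.
- Keep the optional longest-DoR sensitivity analysis.

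The cost is SAP wording and programming, with no new data. Reported DoR may be shorter for some participants.
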